We will minimize these risks by adhering to all entry criteria, not enrolling participants with uncontrolled hypertension or other unstable medication conditions, having same-room observation of all participants during the infusion and for 2 hours post-infusion that includes blood pressure monitoring, oxygen saturation monitoring, and management of psychotomimetic adverse effects by highly trained and psychologically-informed nursing and medical support staff. We will also use clonidine as needed the day of infusion (if determined to not increase risk of hypotension or orthostasis; see below).

Plans to ensure cardiovascular safety during the ketamine infusions: The most frequent cardiovascular effect of ketamine infusion is increase in blood pressure. A study of 66 patients, mean age 57, 38% with controlled hypertension and excluding patients with either a systolic BP >160 mmHg or diastolic BP > 100 mmHg at baseline, reported blood pressure effects of 684 IV ketamine infusions (Riva-Posse et al, Blood pressure safety of subanesthetic ketamine for depression: a report on 684 infusions. J Affect Disord 2018). In 9% of infusions a blood pressure measurement that was greater than 30 mmHg systolic or 15mmHg diastolic was recorded although there was no measurement that was greater than 45mmHg systolic or 30mmHG diastolic over baseline. The blood pressure increases were transitory. No patient required an intervention to treat blood pressure.

In this study the mean age of the patient group is anticipated to be 10-13 years older than the patient group in the Riva-Posse study and it is also anticipated that the rate of controlled hypertension will be higher. There are several procedures to increase safety in this study.

1. Participants with uncontrolled hypertension, defined as baseline systolic BP > 150 systolic or 90 diastolic, will be excluded.
2. Participants will be routinely pre-treated with clonidine 0.1mg the night before treatment and the morning of treatment, unless otherwise indicated (e.g., baseline BP is below 110 systolic or 70 diastolic).

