3. Prior to each infusion BP will be measured after the patient has been lying quietly for 5 minutes. This recording will be the baseline BP. If baseline BP is elevated (Systolic > 160 or Diastolic >95), oral clonidine 0.1 mg will be administered and BP will be re-checked 20-30 minutes later. The dose of clonidine may be increased up to 0.2-0.3 mg depending upon participant benefit and tolerability. If BP continues to be elevated (Systolic > 160 or Diastolic >95), ketamine infusion will not be administered that day.
4. During the IV ketamine infusion BP is recorded every 10 minutes. A measurement that shows a BP increase over 25% from systolic or diastolic baseline and reaches a level of 175 systolic or 105 diastolic will trigger a repeat measurement in two minutes. If the same increase is recorded, then oral clonidine 0.1 mg will be given. If increased blood pressure measurements persist (above 175 systolic or 105 diastolic) the infusion will be discontinued.

5. If BP increases to levels described in #3 or participants experience psychotomimetic/dissociative effects, prior to the subsequent ketamine infusion, oral clonidine 0.1 mg will be taken by participants the night before the infusion and at least 30 minutes prior to the infusion. The dose of clonidine may be increased up to 0.2-0.3 mg, depending upon participant benefit and tolerability, for a maximum total daily dose of 0.6 mg when clonidine is used by the team for pre-treatment (night before/morning of). (Lenze et al, Ninety-six hour ketamine infusion with co-administered clonidine for treatment-resistant depression; World J Biol Psychiatry 2016).
6. An ECG will be done at baseline, at the end of continuation and at the end of the maintenance or at time of reoccurrence of depression

Plans to monitor and minimize psychotomimetic/dissociative effects:

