3.4.2. Clonidine Co-administration

In order to prevent or reduce the severity of the psychotomimetic/dissociative and hypertensive effects of ketamine, Clonidine(0.1mg) is recommended to be routinely co-administered with ketamine. Clonidine co-administration does not alter the antidepressant activity of ketamine in either preclinical or clinical studies.

We will measure doses of clonidine co-administration and, if not used, reasons why it is declined.

4. Statistical principles

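### The in-infusion blood pressure trigger (Protocol II.G, item 4) is loosest for participants who start highest, and does not match its own stop level above a start of 140/84

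*Protocol*

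**What the plan says.** The rules are in Protocol II.G, in the numbered list on cardiovascular safety during infusions.

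- **Start (item 3).** The resting reading before each infusion is the baseline. If it is above 160 systolic or 95 diastolic, clonidine is given and the pressure is rechecked after 20-30 minutes. Then: "If BP continues to be elevated (Systolic > 160 or Diastolic >95), ketamine infusion will not be administered that day". A start at exactly 160/95 is allowed.
- **Trigger (item 4).** Pressure is recorded every 10 minutes. The two-minute repeat is prompted by "A measurement that shows a BP increase over 25% from systolic or diastolic baseline and reaches a level of 175 systolic or 105 diastolic". If the repeat shows the same increase, oral clonidine 0.1 mg follows.
- **Stop (item 4, last sentence).** "If increased blood pressure measurements persist (above 175 systolic or 105 diastolic) the infusion will be discontinued". No percentage appears here.
- **Next infusion (item 5).** Clonidine is taken beforehand: "If BP increases to levels described in #3 or participants experience psychotomimetic/dissociative effects, prior to the subsequent ketamine infusion".
- **Pre-treatment (item 2).** "Participants will be routinely pre-treated with clonidine 0.1mg the night before treatment and the morning of treatment, unless otherwise indicated". The clonidine paragraph later in II.G is narrower. It limits use to participants who have had infusion-related pressure rises or psychotomimetic effects.

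The background to the list cites a report of 684 infusions, with rises above 30 systolic or 15 diastolic in 9% of infusions, "although there was no measurement that was greater than 45mmHg systolic or 30mmHG diastolic over baseline". The protocol expects its own participants to be 10-13 years older, and "it is also anticipated that the rate of controlled hypertension will be higher".

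**The concern.** A relative condition joined to an absolute one by 'and' can never make a rule act sooner. It can only delay action, and here the delay falls on participants who start with the highest pressure. For them the trigger for the mildest response (a second reading, then a small oral dose) sits above the level that the same item uses for stopping the infusion. Staff facing one reading could reasonably do nothing under item 4, or go straight to stopping.

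At stake is the consistent handling of the cardiovascular effect that the protocol itself calls the most frequent, in a population expected to have more controlled hypertension than the cited one.

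**Working it through.** The plan gives no derived figure to reproduce: 25%, 175/105 and 160/95 are set values. The check is arithmetic on the rule.

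**Inputs.** Trigger: rise over 25% and 175 systolic or 105 diastolic (item 4). Highest permitted start: 160/95 (item 3). The 150/90 limit (exclusion criterion 4; II.G item 1) applies at evaluation, not on the infusion day. Largest rises in the cited report: 45 systolic, 30 diastolic.

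**Step 1: where the 25% condition starts to matter.** Divide each level by 1.25: 175/1.25 = 140 and 105/1.25 = 84. Below these starts, any reading at 175 or 105 is already a rise of more than 25%, so the condition is redundant.

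**Step 2: effective trigger.** Judging each component against its own baseline, the trigger is max(175, 1.25 × systolic start) and max(105, 1.25 × diastolic start).

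| Start | 1.25 × start | Effective trigger | Excess over 175/105 |
|---|---|---|---|
| 130/80 | 162.5/100 | 175/105 | 0/0 |
| 140/84 | 175/105 | 175/105 | 0/0 |
| 145/87 | 181.25/108.75 | 181.25/108.75 | 6.25/3.75 |
| 150/90 | 187.5/112.5 | 187.5/112.5 | 12.5/7.5 |
| 160/95 | 200/118.75 | 200/118.75 | 25/13.75 |

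**Step 3: a worked reading.** Start 160/95, reading 199/118. Systolic: 199/160 = 1.244, a rise of 39 mmHg. Diastolic: 118/95 = 1.242, a rise of 23 mmHg. Neither exceeds 25%, so nothing is triggered. Both rises are within the cited report's maxima of 45 and 30.

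**Step 4: does another reading of the 'and' rescue it?** Suppose one component may supply the 25% and the other the level. Some cases then do trigger. From 160/70, a reading of 180/90 has 90/70 = 1.286 and reaches 175. The example in step 3 still fails, because neither component is up by more than 25%.

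**Step 5: the stop sentence for the same participant.** It follows the repeat and clonidine steps in the text.
- Read as the last step of that sequence, it is not reached at 199/118, because the sequence never began.
- Read alone, a persisting 199/118 stops the infusion, but without the two-minute confirmation and clonidine that a participant starting at 130/80 would have had first.

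The text does not say which is meant.

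**The case against.** The strongest reply is that the stop limit carries no percentage. On its plain words, a persisting 199/118 ends the infusion whatever the start, and readings every 10 minutes would show persistence. This stands in part. A reader might infer that pressures up to 200/118.75 are unprotected, and the documents do not support that. What is certainly lost is the two-minute repeat and the mandatory dose.

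Second, other safeguards exist. Protocol II.F.2 and II.G allow as-needed clonidine on the infusion day, at up to 0.3 mg for pressure control. Participants are observed in the same room, and discharge waits for any pressure elevation to normalize. Item 5 would bring clonidine before the next infusion, since 199/118 exceeds item 3's levels. So 'no clonidine' would be too strong: it is only not mandated by item 4. But none of these sets a numeric trigger during the current infusion.

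Third, a reader might infer that these readings drop out of the safety results, because the SAP tracks clonidine use ("We will measure doses of clonidine co-administration and, if not used, reasons why it is declined") and, in 4.2.2, reasons for incomplete infusions. That does not follow. Pressure is recorded regardless of item 4, SAP 5.5.1 adopts the infusion monitoring schedule, and the adverse event definition in Protocol III.B applies whether or not item 4 acts.

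Fourth, item 3 does not flatly refuse a start at 161/96. It gives clonidine and rechecks, so a direct contrast with 199/118 would be unfair.

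Finally, requiring a relative rise could be a deliberate choice, to avoid reacting to a modest change in someone who starts high. Without it, a rise of 15/10 from 160/95 would prompt action. But that action is a second reading and, if confirmed, 0.1 mg of clonidine. The protocol has already chosen 175/105 as its stop level for every start.

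**Conclusion.** The concern holds as a defect in the trigger and an inconsistency with the stop sentence. For starts above 140/84, the trigger rises by up to 25 mmHg systolic and 13.75 mmHg diastolic at the highest permitted start. On one reading of the stop sentence these participants get no item 4 action in that range. On the other they are stopped without the intermediate steps. Neither is a sensible design.

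The figures are exact, given two assumptions: each component is judged against its own baseline, and the baseline is the pressure at which the infusion starts. Item 3 does not say whether a recheck after clonidine replaces the first reading. If it does not, a first reading of 170/100 that settles to a permitted start would put the trigger at 212.5/125.

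The number of infusions affected cannot be stated. The documents give no distribution of pre-infusion pressure and no size for clonidine's effect on the rise, so any count would reflect assumed inputs.

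**What to change.** Amend the trigger in item 4 so that it matches the stop level. For example: 'Any reading at or above 175 systolic or 105 diastolic is repeated two minutes later; if it is confirmed, clonidine 0.1 mg is given by mouth.'

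Leave the stop sentence unchanged. In particular, do not add a 10-minute deadline to it: that would alter the rule for every participant, and is shorter than the 20-30 minutes that item 3 allows before rechecking after clonidine. If a relative rise is still wanted, a rise over 25% can stay as a separate prompt for a repeat reading.

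The cost is a short protocol amendment, with no new visit or equipment. In participants who start above 140/84 there will be some extra repeat readings and 0.1 mg doses, and possibly a few more stopped infusions. Below 140/84 the trigger is unchanged, apart from any extra repeat readings if the 25% prompt is kept.

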2.2. Objectives

2.2.1. Objectives and study aims

The study aims to learn whether it is feasible to conduct a larger, longer trial in the future to learn about the long-term effects of ketamine infusions. In addition, this study will develop and utilize innovative methodological approaches to demonstrate the feasibility of precision medicine and mHealth approaches in depression treatment.

The study will also provide preliminary data on response and remission rates, adverse events, and cognitive changes with ketamine during a 4-week acute phase, 4-week continuation phase, and 3-month post-infusion follow-up phase.

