- 8) Review of medical conditions: *Must not have any medical conditions affecting IV ketamine safety or tolerability or that would interfere with participation in a long-term study. (i.e., life expectancy < 1 year because of terminal illness, unstable angina). Must not have inadequately controlled hypertension.*

D. Schedule of Measures

SCHEDULE OF MEASURES				FOLLOW – UP +++		
	BASELINE	ACUTE END (WK 4)*	CONTINUATION END (WK 8)**	1 MONTH	2 MONTH	3 MONTH
Screening						
SCID-5+	X					
PHQ-9	X			X	X	X
ATHF	X					

Short Blessed Test	X					
Blood Pressure	X					
AUDIT	X					
DAST	X					
CIRS-G	X					
Outcomes						
MADRS	X	X	X	X	X	X
Scale for Suicidal Ideation (SSI)	X	X	X			
Psychological well-being (NIH Toolbox)	X	X	X			
Cognitive Battery (NIH Toolbox)	X	X	X			
Miro Health Cognitive Battery	X	X	X			
Pittsburgh Sleep Quality Index (PSQI)++	X	X	X			
Safety						
AE Monitoring	X	X	X			
Medication List	X	X	X			
Medical History	X					
Height/Weight	X		weight			
ECG	X		X			
Blood Chemistries***	X		X			
Craving Scale	X	X	X			
Depression daily self-reports	THROUGHOUT					

*Acute End assessments will take place after at least 4 weeks of treatment or upon early termination from Acute phase. There may be some delays between baseline assessments and the start of treatment.

**Continuation End assessments will take place after the 8th week of treatment or upon early termination from Continuation phase.

*** Blood chemistries may include CBC, BMP (including LFTs); and TSH at baseline if not obtained within the last 6 months.

+Subset of SCID-5 will be administered to assess Bipolar And Related Disorders, Depressive Disorders, Schizophrenia And Other Psychotic Disorders

++Item 6 of PSQI will be administered.

+++ Follow-Up assessments (typically phone) will be conducted for participants who begin Continuation Phase at 1, 2, and 3 months after their last study visit (Wk 8, or their last study visit if the participant ends early)

E. Determination of Remission

1. Acute Phase End

Participants who complete the acute phase and reach a MADRS score indicating remission (<10) or response (30% reduction) will continue IV ketamine for 4 weeks. This continuation phase is needed to establish the stability of remission/response.

Participants without a 30% reduction in MADRS score at the end of the acute phase will not proceed to the Continuation Phase of the study; their participation will end.

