5.1. Outcome definitions

Remission from depression is defined as MADRS score 0-9 at Week 4(acute phase end).

Response to treatment is defined as $\geq 30\%$ reduction in depressive symptoms on the MADRS from baseline to Week 4.

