5.1.1. Primary outcomes

Remission from Depression at Week 4.

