5.1.2. Outcome measurements

Change in Depression Severity as measured by MADRS at Week 4 and 8.

Change in Psychological Well-Being as measured by NIH Toolbox Psychological Well-Being Surveys, Positive Affect and General Life Satisfaction at Week 4 and 8.

Change in Cognition as measured by NIH Toolbox and Miro Health Cognitive Batteries at Week 4 and 8.

Change in Executive Function as measured by NIH Toolbox and Miro Health Cognitive Batteries at Week 4 and 8.

Change in Suicidal Ideation as measured by Scale for Suicidal Ideation at Week 4 and 8.

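### SAP 2.2.1 promises response and remission rates through the 3-month follow-up, but neither is defined after Week 4, the denominator is ambiguous, and treatment started during follow-up is not systematically captured

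*SAP*

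**What the plan says.** **Objective.** SAP 2.2.1 commits the study to "preliminary data on response and remission rates, adverse events, and cognitive changes with ketamine during a 4-week acute phase", then to the same through the "4-week continuation phase, and 3-month post-infusion follow-up phase".

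**Outcomes.** SAP 5.1 defines remission as a MADRS score of 0 to 9 at Week 4. It defines response as a 30% or greater "reduction in depressive symptoms on the MADRS from baseline to Week 4". The primary outcome in SAP 5.1.1 is "Remission from Depression at Week 4". The secondary measures in SAP 5.1.2 stop at Week 8, for example "Change in Depression Severity as measured by MADRS at Week 4 and 8".

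**Data collected.** The Schedule of Measures (Protocol II.D) marks the MADRS at baseline, Week 4, Week 8 and months 1, 2 and 3. It marks the Medication List at baseline, Week 4 and Week 8 only.

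**Who is followed.** A footnote to that schedule reads: "Follow-Up assessments (typically phone) will be conducted for participants who begin Continuation Phase at 1, 2, and 3 months after their last study visit". Protocol II.E and SAP 3.1 end participation for anyone who does not reach the MADRS threshold at the end of the acute phase.

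**Who is analysed.** SAP 4.3 takes in everyone who was infused at least once. SAP 3.1 counts people who withdraw during the acute phase as neither responding nor remitting.

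**The concern.** A stated objective has data behind it but no outcome definition, time point or denominator. Two people could follow this SAP and report quite different month-3 remission rates. With so few participants, the choice might be made after the results are known.

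The missing medication record is a different kind of gap. A definition can be added before analysis, but treatment that nobody asked about at the calls cannot be recovered later. Suppose a participant scores below 10 on the MADRS at month 3. If it is unknown whether that person has since started ketamine elsewhere, esketamine, ECT, TMS or a new antidepressant, the score says little about whether the benefit of the infusions has lasted.

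**Working it through.** The plan gives no figure for follow-up, so there is none to reproduce. The check sets the sections side by side and then illustrates the size.

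**1. Time points**

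| Item | Baseline | Week 4 | Week 8 | Months 1, 2, 3 |
|---|---|---|---|---|
| MADRS collected (Protocol II.D) | yes | yes | yes | yes |
| Response and remission defined (SAP 5.1) | reference | yes | no | no |
| MADRS change listed as outcome (SAP 5.1.2) | reference | yes | yes | no |
| Medication List marked (Protocol II.D) | yes | yes | yes | no |

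SAP 5.2 plans descriptive rates and a mixed-effect model but names no time points, so it does not fill the gap. Week 8 is affected too: Protocol II.E and SAP 3.1 assess remission and response at the end of Continuation, and SAP 2.2.2 hypothesises continuation efficacy in those terms, yet SAP 5.1 stops at Week 4.

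**2. Denominator.** Follow-up covers Continuation entrants, and the analysis population is everyone infused. SAP 4.2.2 says follow-up data are gathered whatever the adherence. That concerns adherence to treatment and does not bring acute non-responders back into follow-up.

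**3. Size of the denominator effect (illustration).** From the documents: N = 25 (SAP 3.1) or N = 15 (Protocol II.B). Assumed: 40%, 60% or 80% enter Continuation, and about half of those are in remission at a follow-up call. With m followed and x in remission, the two rates are x/m and x/N, the second counting non-continuers as not in remission. Exact 95% limits are Beta⁻¹(0.025; x, n−x+1) and Beta⁻¹(0.975; x+1, n−x), with n the denominator used.

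| N | m | x | Among followed, x/m (95% CI) | Among all infused, x/N (95% CI) | Difference (points) |
|---|---|---|---|---|---|
| 25 | 10 | 5 | 50% (19–81) | 20% (7–41) | 30 |
| 25 | 15 | 8 | 53% (27–79) | 32% (15–54) | 21 |
| 25 | 20 | 10 | 50% (27–73) | 40% (21–61) | 10 |
| 15 | 6 | 3 | 50% (12–88) | 20% (4–48) | 30 |
| 15 | 9 | 4 | 44% (14–79) | 27% (8–55) | 18 |
| 15 | 12 | 6 | 50% (21–79) | 40% (16–68) | 10 |

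Counting non-continuers as failures is a convention, because nobody rates them. If their status is treated as unknown, the all-infused rate in the second row could lie anywhere from 8/25 = 32% to (8 + 10)/25 = 72%.

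**4. Effect of later treatment (illustration).** Take the second row and assume that 2 of the 8 in remission had started a new treatment. Remission without new treatment is 6/15 = 40% of those followed and 6/25 = 24% of all infused, against 8/15 = 53% and 8/25 = 32%. Without a medication record these cannot be told apart.

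**The case against.** The strongest reply is that this is a descriptive feasibility pilot. Its hypotheses concern acute and continuation efficacy, its Week 4 primary outcome is not in question, and persistence of benefit is naturally studied in those who had benefit. A rate among Continuation entrants is a legitimate conditional rate. All of that stands, and it limits the weight of the point. It does not remove the need for a definition and a labelled denominator, because a descriptive rate needs both.

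A second reply is that later treatment could surface through adverse event reporting: worsening of an existing illness counts as an event, and the action taken is recorded. That route is incidental. The schedule marks no adverse event monitoring at follow-up, and its footnote treats the last study visit as Week 8 or an earlier end. Protocol III.B and III.D collect events to the last visit or last assessment, which sits uneasily with those blanks. Still, the reply is right that no section says later treatment goes unrecorded. The gap is inferred from the schedule.

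A reader might also infer four stronger things that the documents do not support:

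- That following the SAP means discarding the month 1 to 3 ratings. SAP 2.2.1 commits to reporting them and SAP 5.2 does not exclude them; they are simply unspecified.
- That durability is the main input to the future trial. SAP 2.2.1 puts feasibility first, and Protocol III.E speaks of feasibility and a positive signal.
- That the reported rate must be biased upward. A conditional rate labelled as such is not inflated, and someone who starts a new treatment but still scores badly does not raise the rate.
- That the PHQ-9, taken at follow-up but not at Week 4 or Week 8, leaves follow-up without a comparator. The MADRS, which defines both outcomes, is taken at all six time points.

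**Conclusion.** The point holds. The objective, the outcome definitions and the schedule do not match: response and remission are promised through three months off infusions, defined at Week 4 only, and measurable at months 1, 2 and 3 in Continuation entrants only. The denominator is ambiguous, and treatment started during follow-up is not systematically captured.

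Under the assumptions shown, the denominator alone shifts the follow-up remission rate by about 10 to 30 percentage points. Those percentages illustrate the issue and do not predict the trial's results; the acute response rate, the share in remission and the number newly treated are all assumed. The finding about the Medication List assumes that the Schedule of Measures is a complete list of what is collected at the calls. The change should be made, chiefly because the medication information cannot be recovered afterwards.

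**What to change.** 1. **Schedule of Measures.** Mark the Medication List at the three existing follow-up calls, asking about any ketamine, esketamine, ECT, TMS or new antidepressant since the last contact.
2. **SAP 5.1.** Extend the MADRS response and remission definitions to Week 8 and to months 1, 2 and 3, always against study baseline.
3. **SAP 5.2.** Report each follow-up rate twice: among Continuation entrants, labelled as conditional on entering Continuation, and among all infused, with non-continuers counted as not in response or remission. The second agrees with SAP 4.3 and extends the rule for acute-phase withdrawals in SAP 3.1. Beside each rate, give the number in response or remission who had started new treatment and the number actually rated at that call, since SAP 5.3 has no rule for missed calls.

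The sentence in SAP 2.2.1 also promises adverse events and cognitive changes through follow-up, and the schedule marks neither there. Its wording should be reconciled with the schedule at the same time.

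The cost is a few SAP lines, a minor schedule amendment and a few questions at calls that already take place. No visit is added. The reported follow-up rate may look less favourable.
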